1.0 TRIAL SUMMARY

Abbreviated Title	Effect of pembrolizumab (Keytruda®) on biomarkers in early breast cancer.
Trial Phase	Retrospective study and phase 0 (window-of-opportunity) study
Clinical Indication	Treatment of patients with early breast cancer
Trial Type	Retrospective cohort study and nonrandomized trial
Type of control	NA
Route of administration	Intravenous administration
Trial Blinding	Open label trial
Treatment Groups	Patients with early breast cancer
Number of trial subjects	200 subjects will be included in the retrospective cohort; 54 in the phase 0 trial
Estimated enrollment period	18 months for the phase 0 trial
Estimated duration of trial	24 months
Duration of Participation	6-7 weeks
Estimated average length of treatment per patient	1 day

2.0 TRIAL DESIGN

2.1 Trial Design :

The study consists of 2 parts: a retrospective study, and a prospective clinical study with pembrolizumab (Keytruda®) (Phase 0).

1/ Retrospective study (S58910):

This is a retrospective analysis to study the expression of PD-L1 in ER/PR negative breast tumors and to correlate this PD-L1 expression with tumor infiltrating lymphocytes (TILs), proliferation, expression of apoptosis and clinical outcome (development of distant metastases).

2/ Phase 0 study (S60100):

This is a Phase 0 single center, open-label, non-randomized study in patients with early ER/PR negative breast cancer or early ER positive breast cancer with expression of TILs on core biopsy. Patients will be treated with one injection of Pembrolizumab (Keytruda®) administered intravenously at 200 mg 10 +/- 4 days before surgery. This phase 0 study will consist of 2 cohorts; cohort A will include patients who are scheduled for upfront surgery. Cohort B will include patients who received neoadjuvant chemotherapy (with anti-Her2 therapy if Her2 positive) and who have clear signs of residual tumor on imaging after finishing neoadjuvant chemotherapy (i.e. on imaging estimated residual tumor size of at least 10 mm). The injection will be given in the oncological outpatient unit. Patients will be monitored carefully for the development of adverse experiences/events. Adverse experiences/events will

be evaluated according to criteria outlined in the NCI Common Terminology Criteria for Adverse Events (CTCAE), version 4.0.

Cohort A	Upfront surgery group	Cohort B	Neo-adjuvant group
A1	Triple negative	B1	Triple negative
A2	ER-/PR-/Her2+	B2	ER-/PR-/Her2+
A3	ER+ with TILs on core biopsy	B3	ER+ with TILs on core biopsy

2.2 Trial Diagram phase 0 trial

Trial period	Screening	Administration	Surgery	Post-op
Scheduling window (days)	-14 to 0	0	10 +/-4	30+/-7
Administrative procedures				
Informed consent	x			
Inclusion/exclusion criteria	x			
Demographics and medical history	x			
Prior and concomittant medication review	x	x	x	x
Labo processing/assesment (local)				
Pregnancy test	x			
CBC with differentiation	x		x	x
Chemistry	x		x	x
TSH, (T3, FT4)	x			x
Urinalysis	x		x	x
Labo (central)				
Blood sample	x		x	x
Tumor tissue collection				
Newly/archival tissue collection	x*		x	
Clinical procedures/assesments				
Review adverse events	x		x	x
ECG	x			
Physical examination	x	x	x	x
Vital signs, weight, height	x	x	x	x
ECOG performance status	x			
Pembrolizumab administration		x		
Anti-cancer therapy status				x
Survival status				x

* Only necessary for cohort B, but will be collected as well in cohort A for further research requiring fresh material, in case patients of cohort A are willing to provide a new fresh tumor sample (with biopsy).

3.0 OBJECTIVES & HYPOTHESES

3.1 Primary Objective & Hypothesis

Objective: To evaluate whether one administration of pembrolizumab (Keytruda®) is able to alter biomarkers related to intratumoral immunity (i.e. the amount of TILs, PD-L1 and CD73 expression) and proliferation (i.e. Ki67 expression) in early breast cancer

Hypothesis: One administration of pembrolizumab (Keytruda®) will result in an increase in the amount of TILs and a decrease in the expression of PD-L1, CD73 and Ki67 in a subgroup of patients with early breast cancer.

3.2 Secondary Objectives & Hypotheses

PROSPECTIVE STUDY:

(1) **Objective:** To evaluate whether anthracycline-taxane based neo-adjuvant chemotherapy is able to alter biomarkers related to intratumoral immunity and proliferation in early breast cancer.

Hypothesis: Administration of anthracycline-taxane based neo-adjuvant chemotherapy will result in an increase in the amount of TILs and a decrease in the expression of PD-L1, CD73 and Ki67 in a subgroup of patients with early breast cancer.

(2) **Objective:** To evaluate whether there is a difference in biomarker evolution after pembrolizumab (Keytruda®) administration in cohort A (upfront surgery, not prior treatment) or cohort B (have received full course of neoadjuvant chemotherapy, and have clear evidence of residual tumor after chemotherapy).

Hypothesis: The change in biomarker expression will be higher in cohort B (having received full course of neoadjuvant chemotherapy, and having clear evidence of residual tumor after chemotherapy) than in cohort A (upfront surgery, not prior treatment).

(3) **Objective:** To evaluate whether there is a difference in biomarker evolution after one pembrolizumab (Keytruda®) administration in triple negative breast cancer (Cohort A1,B1) versus ER/PR negative Her2 positive breast cancer (Cohort A2,B2).

Hypothesis: The change in biomarker expression after pembrolizumab (Keytruda®) administration will be higher in triple negative breast cancer than in ER/PR negative Her2 positive breast cancer.

(4) **Objective:** To evaluate whether there is a difference in biomarker evolution after one pembrolizumab (Keytruda®) administration in triple negative breast cancer (Cohort A1,B1) versus ER positive breast cancer (Cohort A3,B3).

Hypothesis: The change in biomarker expression after pembrolizumab (Keytruda®) administration will be higher in triple negative breast cancer than in ER positive breast cancer.

(5) **Objective:** To evaluate whether there is a difference in biomarker evolution after one pembrolizumab (Keytruda®) administration in ER/PR negative Her2 positive breast cancer (Cohort A2,B2) versus ER positive breast cancer (Cohort A3,B3).

Hypothesis: The change in biomarker expression after pembrolizumab (Keytruda®) administration will be higher in ER/PR negative Her2 positive breast cancer than in ER positive breast cancer

(4) **Objective:** To evaluate whether one administration of pembrolizumab (Keytruda®) causes a significant shift in T-cell subsets in peripheral blood.

Hypothesis: One administration of pembrolizumab (Keytruda®) causes a significant shift in T-cell subsets in peripheral blood.

(5) **Objective:** To evaluate whether baseline PD-L1 expression and amount of TILs are predictive for the effect of pembrolizumab (Keytruda®) and/or response to neo-adjuvant chemotherapy.

Hypothesis: Tumors with a high baseline PD-L1 expression and a high amount of TILs are more likely to respond to pembrolizumab (Keytruda®) and/or response to neo-adjuvant chemotherapy than tumors with a low baseline PD-L1 expression and/or a low amount of TILs.

RETROSPECTIVE STUDY:

(6) **Objective:** To evaluate whether baseline expression of PD-L1, CD73, Ki67 and the amount of TILs can predict distant metastasis free survival.

Hypothesis: Low expression of PD-L1, CD73 and Ki67 and a high amount of TILs are associated with a better distant metastasis free survival.

(7) **Objective:** To evaluate whether there is an association between expression of PD-L1, CD73, Ki67 and the amount of TILs.

Hypothesis: There is an association between expression of PD-L1, CD73, Ki67 and the amount of TILs.

(8) **Objective:** To evaluate whether the immunohistochemical analysis of PD-L1, CD73, Ki67 and TIL count on core biopsy specimens reflects accurately the expression of these markers on tumor resection specimen.

Hypothesis: The immunohistochemical analysis of PD-L1, CD73, Ki67 and TIL count on core biopsy specimens reflects accurately the expression of these markers on tumor resection specimen.

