4.2.3 Rationale for Endpoints

4.2.3.1 Biomarker Research

PD-L1: Previous studies have shown a correlation between PD-L1 expression and an objective response in patients treated with anti-PD-1/L1 therapy. However this finding is not consistent among all studies. It also raises the question whether clinical decisions regarding the treatment of patients who have failed conventional therapies and for whom no other treatments are available should be based on PD-L1 expression. On the basis of these controversial results, we will evaluate the potential predictive role of PD-L1 expression in tumor cells.

TILs: TILs might be the primary predictors of response to ICP therapy. Tumors with a large amount of TILs are more likely to respond to anti PD-1/L1 therapy.

Ki67: Immunohistochemical assessment of the proportion of cells staining for the nuclear antigen Ki67 has become the most widely used method for comparing proliferation between tumor samples. In spite of consistent data on Ki67 as a prognostic marker in early breast cancer, its role in breast cancer management remains uncertain. Reductions in Ki67 occur in the tumors of most patients receiving systemic treatment, and there is some evidence that there are greater reductions in patients who respond to treatment.

Except from the above mentioned biomarkers will blood and tissue samples be used to study other possible biomarkers and T-cell subpopulations. These tests will be performed in cooperation with KU Leuven laboratories.

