5.1.2 Subject Inclusion Criteria

In order to be eligible for participation in this trial, the subject must:

1. Be willing and able to provide written informed consent/assent for the trial.
2. Be ≥ 18 years of age on day of signing informed consent.
3. Be willing to provide tissue from a newly obtained core or excisional biopsy of a tumor lesion if needed. *Newly obtained is defined as a specimen obtained up to 6 weeks (42 days) prior to initiation of treatment on Day 0. Subjects for whom newly obtained samples cannot be provided (e.g. inaccessible or subject safety concern) may submit an archived specimen only upon agreement from the Sponsor.*
4. Have a performance status of 0 or 1 on the ECOG Performance Scale.
5. Have non-metastatic operable newly diagnosed primary invasive carcinoma of the breast that is:
 - a. Histologically confirmed
 - b. ER/PR negative or ER positive breast cancer with TIL expression on core biopsy. ER/PR status will be evaluated with Allred score (semi-quantitative measurement) following ASCO CAP guidelines 2009. TIL count based on the guidelines of the International TILS Working Group on Breast Cancer
 - c. HER2 negative or positive. HER2 status will be evaluated using IHC followed by FISH with dual probe (ASCO CAP guidelines 2013).

- d. Primary tumor size greater than 1 cm, measured by any of clinical examination, mammography, ultrasound or magnetic resonance imaging
 - e. Any clinical nodal status
6. Have evaluable core biopsy for IHC
 7. Be willing to provide plasma/blood samples
 8. After neo-adjuvant chemotherapy (cohort B1 and B2) patients must have residual tumor >1cm and must be willing to provide evaluable new tumor biopsy for IHC
 9. Demonstrate adequate organ function as defined in Table 1, all screening labs should be performed within 14 days of treatment initiation.

Table 1 Adequate Organ Function Laboratory Values

System	Laboratory Value
Hematological	
Absolute neutrophil count (ANC)	≥1,500 /mcL
Platelets	≥100,000 / mcL
Hemoglobin	≥9 g/dL or ≥5.6 mmol/L without transfusion or EPO dependency (within 7 days of assessment)
Renal	
Serum creatinine OR Measured or calculated ^a creatinine clearance (GFR can also be used in place of creatinine or CrCl)	≤1.5 X upper limit of normal (ULN) OR ≥60 mL/min for subject with creatinine levels > 1.5 X institutional ULN
Hepatic	
Serum total bilirubin	≤ 1.5 X ULN OR Direct bilirubin ≤ ULN for subjects with total bilirubin levels > 1.5 ULN

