5.2 Trial Treatments

5.2.1 Study cohorts prospective trial

[figure not shown]
- Cohort A1: upfront surgery, triple negative
- Cohort A2: upfront surgery, ER/PR negative, Her2 positive
- Cohort A3: upfront surgery, ER positive with TILs on corebiopsy
- Cohort B1: tumor >1cm after neo-adjuvant anthracycline-taxane based chemotherapy, triple negative
- Cohort B2: tumor >1cm after neo-adjuvant anthracycline-taxane based chemotherapy, ER/PR negative, Her2 positive
- Cohort B3: tumor >1cm after neo-adjuvant anthracycline-taxane based chemotherapy, ER positive with TILs on corebiopsy

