8.0 STATISTICAL ANALYSIS PLAN

8.1 Determination of sample size

Retrospective study (S58910):

Between 2005 and 2010, 285 patients with a ER/PR negative breast cancer larger than 2cm were diagnosed and treated with upfront surgery at the Leuven Multidisciplinary Breast Center (University Hospitals Leuven). Two hundred consecutive patients with available tumor tissue and follow-up data will be included in the proposed retrospective study.

Prospective study (S60100):

The assumptions for the sample size are as follows: More than 600 patients with early breast cancers are diagnosed and treated at the Leuven Multidisciplinary Breast Center (University Hospitals Leuven) on a yearly basis. Twenty percent (120 patients) of these breast cancers are ER/PR negative, half of them Her2 negative and half of them Her2 positive. Of the 120 ER/PR negative patients, 25 percent (30 patients) is expected to receive upfront surgery and 75 percent (90 patients) upfront chemotherapy. After upfront chemotherapy 45 percent of patients is expected to have a residual disease larger than 1cm (40 patients). In total, 70 patients are expected to be eligible for the suggested prospective study. Participation of 50 percent of eligible patients would allow inclusion of 34 patients after 1 year.

Approximately 66 percent (400 patients) of all patients treated at the Leuven Multidisciplinary Breast Center have ER positive breast cancer. 10 percent of these ER+ positive patients is expected to be eligible for this trial taking into account the tumour size after neo-adjuvant therapy and a decent expression of TILs on core biopsy. Participation of 50% of eligible patients would allow inclusion of 20 patients after 1 year. Patients will be included until we have reached the total of 54 patients, independent of the amount of patients in the different cohorts

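### Subtype objectives (4) and (5) compare ER positive tumors entered only with TILs against ER negative tumors entered regardless of TILs, and no planned analysis separates subtype from that selection

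*Combined protocol and SAP*

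**What the plan says.** Section 3.2 uses the numbers (4) and (5) twice. This point concerns the first pair, the subtype comparisons. Objective (4) compares "triple negative breast cancer (Cohort A1,B1) versus ER positive breast cancer (Cohort A3,B3" cohorts; objective (5) compares "ER/PR negative Her2 positive breast cancer (Cohort A2,B2) versus ER positive breast cancer (Cohort A3,B3" cohorts. Hypothesis (4) expects that the change "will be higher in triple negative breast cancer than in ER positive breast cancer", with no mention of TILs, and hypothesis (5) is worded in the same way.

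The entry rule is not the same on the two sides. Section 2.1 admits "early ER positive breast cancer with expression of TILs on core biopsy" alongside ER/PR negative disease, and inclusion criterion 5b in section 5.1.2 reads "ER/PR negative or ER positive breast cancer with TIL expression on core biopsy". In section 5.2.1 the labels of A3 and B3 carry the TIL condition, while the ER negative cohorts do not, for example "Cohort A1: upfront surgery, triple negative".

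Criterion 5b cites a guideline for counting TILs but gives no cut-off. Section 8.1 says only "a decent expression of TILs on core biopsy".

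On the role of TILs, section 4.2.3.1 states: "Tumors with a large amount of TILs are more likely to respond to anti PD-1/L1 therapy". The second objective numbered (5) in section 3.2 makes high baseline TILs, together with high PD-L1, a hypothesis about response to pembrolizumab.

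For between-cohort differences, section 8.2 plans linear models reported as a mean difference in change with a 95% confidence interval. It names no covariates.

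**The concern.** One side of each contrast is selected on a factor that the protocol expects to modify the effect of the drug, and the other side is not. A difference, or the lack of one, could then come from subtype, from TIL selection, or from both, and the planned model cannot tell these apart.

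The result most exposed is a null or reversed one. It could be reported as ER positive disease responding as well as triple negative disease, when the ER positive patients studied were chosen for carrying TILs. This is a matter of who is compared. It would remain if TILs were measured without error and on a separate baseline core.

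**Working it through.** **1. The plan's own figure.** Section 8.1 derives 54 from expected recruitment.
- ER/PR negative: 600 × 0.20 = 120. Upfront surgery: 120 × 0.25 = 30. Chemotherapy first: 120 × 0.75 = 90, of whom 90 × 0.45 = 40.5 (stated as 40) have residual disease above 1 cm. Half of 30 + 40 is 35, against 34 stated.
- ER positive: 400 × 0.10 × 0.5 = 20, as stated.
- Total: 34 + 20 = 54, or 55 from the unrounded steps.

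The figure reproduces to within about one patient. It is a feasibility count: no alpha, power, effect size or SD is given, and there are no cohort quotas.

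**2. Precision of the contrasts.** Section 8.1 splits ER/PR negative disease evenly by HER2. If enrolment follows that split, 34 / 2 = 17 patients stand on the ER negative side of each contrast, against 20 ER positive.
- SE = √(1/17 + 1/20) = 0.33 SD
- 95% CI half-width = 1.96 × 0.33 = 0.65 SD
- Difference needed for 80% power = (1.96 + 0.84) × 0.33 = 0.92 SD

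**3. How far one-sided selection could move a contrast.** The assumptions here are mine and not in the documents. Baseline TILs are normal with SD 1. ER positive tumors start g SD lower than the ER negative comparator. Only the top share p of ER positive tumors by TILs is admitted. Change, taken in the hypothesised direction, correlates ρ with baseline TILs. There is no subtype effect at a given TIL level.

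Lift from selection = φ(t)/p, with t = Φ⁻¹(1 − p).
Expected contrast (ER negative minus ER positive) = −ρ × (lift − g).

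With ρ = 0.5, in SD:

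| Share admitted | Lift | g = 0 | g = 0.5 | g = 1 |
|---|---|---|---|---|
| 90% | 0.19 | −0.10 | +0.15 | +0.40 |
| 75% | 0.42 | −0.21 | +0.04 | +0.29 |
| 50% | 0.80 | −0.40 | −0.15 | +0.10 |
| 25% | 1.27 | −0.64 | −0.39 | −0.14 |
| 10% | 1.75 | −0.88 | −0.63 | −0.38 |

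The two extremes worked through:
- p = 0.10, g = 0: 0.1755 / 0.10 = 1.755, and −0.5 × 1.755 = −0.88.
- p = 0.90, g = 1: 0.1755 / 0.90 = 0.195, and −0.5 × (0.195 − 1) = +0.40.

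The g = 0 column is the part due to selection alone. It shrinks to zero as the criterion comes to admit everyone. The other columns add the natural TIL gap between subtypes, which pulls the other way. With ρ = 0.3 the g = 0 column runs from −0.06 to −0.53.

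**4. Effect on the planned model, and what a covariate does.** Simulation of 17 versus 20 patients, 4,000 runs, ρ = 0.5:
- No subtype effect, g = 0, top half admitted: mean unadjusted contrast −0.39 SD, two-sided 5% test rejects in 22% of runs. Top quarter admitted: −0.64 SD and 51%.
- The same two settings with baseline TILs in the model: mean about 0, rejection about 5%.
- True subtype effect of 0.5 SD: the unadjusted contrast averages 0.10 SD (g = 0, top half) or 0.11 SD (g = 0.5, top quarter). The adjusted one averages 0.50 SD in both, with power of about 32%.

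The covariate model is exactly right in this simulation (linear, same slope in both groups), so this is the best case for adjustment.

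**The case against.** **The restriction is disclosed.** Both objectives name cohorts A3 and B3, whose labels state the TIL condition, and section 4.2.1 explains why ER positive disease is admitted on that basis. This stands for the objectives. It does not reach the hypotheses, which speak of ER positive breast cancer without restriction, or the analysis.

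**The direction is not established.** Section 4.2.1 calls ER positive disease generally less immunogenic and places heavy infiltration mainly in ER/PR negative tumors. Selecting ER positive tumors on TILs may bring the groups closer together. This stands. A reader might infer that the ER positive group must be richer in TILs and that the bias must run against the hypotheses; the documents do not show that. For change in TILs itself, regression to the mean after selection on the baseline value could also act the other way.

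**The premise is tentative.** Section 4.2.3.1 introduces TILs as possible predictors, the formal hypothesis is joint with PD-L1, and response is not the same as change in TILs, PD-L1, CD73 or Ki67. This is fair, and it is why ρ is an assumption. But the trial sets out to test baseline TILs as a predictor, so its subtype contrasts should not leave them out.

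**Two stronger readings fail.** Section 8.1 expects 10% of ER positive patients to be eligible, and a reader might infer that TIL selection removes the other 90%. That figure combines TILs with tumor size after neoadjuvant therapy, so it does not measure TIL selection. A reader might also infer that the contrasts would show a difference whenever TILs matter and subtype does not. In the illustration the test rejects in 22% or 51% of runs, depending on strictness, and less often if ER positive tumors start lower in TILs.

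**The contrasts are secondary and imprecise.** At 17 versus 20 a null result says little in any case. This limits the weight of the point, but the remedy is cheap.

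**Conclusion.** The concern holds in a limited form. TILs are an entry condition on one side only of contrasts (4) and (5), the protocol hypothesises that TILs predict response, and the planned models do nothing about the imbalance. As planned, the contrasts do not isolate subtype and do not support hypotheses worded for ER positive disease in general. They remain readable as comparisons with ER positive tumors that carry TILs.

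Neither the size nor the sign of the distortion can be fixed from the documents. The selection part is near zero if any TILs qualify. At ρ = 0.5 the net distortion, relative to a comparison at equal baseline TILs, runs from about −0.9 SD (equal starting distributions, strict selection) to +0.4 SD (ER positive starting 1 SD lower, lenient selection). That is about −2.7 to +1.2 standard errors of 0.33 SD. The range rests on the assumed correlation, normal TILs and the 17 versus 20 split. Objective (3), triple negative versus HER2 positive, is not affected.

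**What to change.** (a) In objectives, hypotheses and conclusions (4) and (5), name the comparator as ER positive with TILs on core biopsy.

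(b) In section 8.2, keep the all-patient contrast and add a version of the linear model with baseline TILs as a covariate. This keeps every patient.

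(c) As a sensitivity analysis, report both contrasts within tumors meeting the same TIL criterion. Apply to A1, A2, B1 and B2 the threshold used to qualify A3 and B3, and the same core. Both need to be written down first: no threshold is stated, and the B3 label does not say whether the diagnostic or the post-chemotherapy core counts.

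Cost: wording and one extra table. No new staining is needed, because criterion 6 requires an evaluable core from every patient and TILs are among the primary biomarkers in section 3.1.

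Downside: the restricted contrast uses fewer patients and has a wider interval. If TILs are part of how the subtypes differ, the adjusted contrast answers a narrower question than the unadjusted one, so both should be shown.

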5.1.3 Subject Exclusion Criteria

The subject must be excluded from participating in the trial if the subject:

1. Is currently participating and receiving study therapy or has participated in a study of an investigational agent and received study therapy or used an investigational device within 4 weeks of receiving the treatment dose.
2. Has a diagnosis of immunodeficiency or is receiving systemic steroid therapy or any other form of immunosuppressive therapy within 7 days prior to receiving the trial treatment.
3. Has a known history of active TB (Bacillus Tuberculosis)
4. Hypersensitivity to pembrolizumab or any of its excipients.
5. Has had a prior anti-cancer monoclonal antibody (mAb) within 4 weeks (or except for Trastuzumab within 2 weeks) prior to study Day 1 or who has not recovered (i.e., \leq Grade 1 or at baseline) from adverse events due to agents administered more than 4 weeks earlier.
6. Has had prior chemotherapy, targeted small molecule therapy, or radiation therapy within 2 weeks prior to study Day 0 or who has not recovered (i.e., \leq Grade 1 or at baseline) from adverse events due to a previously administered agent.
 - Note: Subjects with \leq Grade 2 neuropathy are an exception to this criterion and may qualify for the study.
 - Note: If subject received major surgery, they must have recovered adequately from the toxicity and/or complications from the intervention prior to starting therapy.
7. Has a known additional malignancy that is progressing or requires active treatment. Exceptions include basal cell carcinoma of the skin or squamous cell carcinoma of the skin that has undergone potentially curative therapy or in situ cervical cancer.
8. Has active autoimmune disease that has required systemic treatment in the past 2 years (i.e. with use of disease modifying agents, corticosteroids or immunosuppressive

drugs). Replacement therapy (eg., thyroxine, insulin, or physiologic corticosteroid replacement therapy for adrenal or pituitary insufficiency, etc.) is not considered a form of systemic treatment.

9. Has known history of (non-infectious) pneumonitis that required steroids or current pneumonitis.
10. Has an active infection requiring systemic therapy.

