5.2.2 Study cohorts prospective trial

The trial design for each cohort is displayed below.

All patients will receive 1 administration of pembrolizumab 10 +/- 4 days before surgery

Cohort A

Cohort B

Patients must:

- Have ER/PR negative or ER positive breast cancer > 1 cm, **and**
- Have received anthracycline-taxane neo-adjuvant chemotherapy, **and**
- Have residual tumor > 1 cm after neo-adjuvant chemotherapy, **and**
- Provide evaluable new tumor biopsy for IHC, **and**
- Provide a blood sample

Patients will be enrolled

D0: administration of Pembrolizumab 200 mg

D10 ± 4: surgery + provide blood sample

Trial treatment should begin on the day of randomization or as close as possible to the date on which treatment is allocated/assigned.

New tumor biopsy only necessary for cohort B, but will be collected as well in cohort A for further research requiring fresh material, in case patients of cohort A are willing to provide a new fresh tumor sample (with biopsy).

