7.1.5.1 Screening

7.1.5.1.1 Patients with ER/PR negative OR ER positive with TILs on core biopsy, and residual tumour of at least 1 cm after neo-adjuvant chemotherapy will be screened before surgery as well as patients with ER/PR negative breast cancer only scheduled for surgery and adjuvant therapy if applicable. Screening Period

Patients will be screened at a maximum of 14 days before administration of Pembrolizumab.

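### Peripheral-blood T-cell objective: the draw windows leave recovery from chemotherapy (cohort B) and surgery as possible explanations of a before/after shift, and fixed draw times would narrow this

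*Combined protocol and SAP*

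**What the plan says.** The objective is the second one numbered (4) among the prospective objectives in 3.2. It is worded causally: one dose "causes a significant shift in T-cell subsets in peripheral blood". It is not split by cohort.

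The timing rules are spread over several sections:

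- **Visit windows (2.2, repeated in 6.0).** Screening, administration, surgery and post-op have the windows "Scheduling window (days) -14 to 0 0 10 +/-4 30+/-7".
- **Central blood (2.2 and 6.0).** It is marked at screening, surgery and post-op. No central sample is marked at the administration visit.
- **Screening (7.1.5.1).** "Patients will be screened at a maximum of 14 days before administration of Pembrolizumab".
- **Chemotherapy washout (5.1.3, criterion 6).** A patient is excluded who "Has had prior chemotherapy, targeted small molecule therapy, or radiation therapy within 2 weeks prior to study Day 0". The interval runs to Day 0, not to the blood draw.
- **Cohort B (2.1 and 5.2.2).** Patients must "Have received anthracycline-taxane neo-adjuvant chemotherapy" and "have clear signs of residual tumor on imaging after finishing neoadjuvant chemotherapy". In 5.2.2 a blood sample is listed among the requirements that precede enrolment and Day 0.
- **First post-dose sample (5.2.2).** "D10 ± 4: surgery + provide blood sample", with no order given between the draw and the operation.
- **Analysis (8.2).** Within-patient change from before to after pembrolizumab is tested with a paired t-test or a Wilcoxon signed rank test, and cohorts are compared with linear models. T-cell subsets, the choice of post-dose sample and time since chemotherapy are not mentioned.

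**The concern.** Every patient is dosed and there is no comparison group. A paired test shows whether the later sample differs from the earlier one. It cannot show whether the drug, recovery from chemotherapy or the operation produced the difference. Attribution therefore depends on the two draws being placed so that as little else as possible changes between them.

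The windows do not secure this. In cohort B the baseline may fall shortly after chemotherapy and the later samples well after it, so T-cell subsets could move through recovery alone. In both cohorts the post-op sample follows surgery, and the surgery-day sample may or may not. Section 4.2.1 hopes that biomarker changes may lead to a blood-based marker to predict benefit and monitor therapy, so a wrong attribution could carry into later work.

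**Working it through.** The plan states no figure for this objective, so there is none to reproduce. The check is date arithmetic on the stated windows.

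**Inputs.** Screening draw: day -14 to 0 (2.2, 7.1.5.1). Washout: 14 days before Day 0 (5.1.3). Surgery: day 10 ± 4, so day 6 to 14. Post-op visit: day 30 ± 7, so day 23 to 37, counted from the dose as 7.1.5.3.1 indicates.

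**Intervals as the plan stands**

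1. Last chemotherapy to baseline blood, minimum = washout minus earliest screening = 14 - 14 = 0 days. If baseline is drawn on day 0, the minimum is 14 days. No maximum is stated.
2. Last chemotherapy to surgery-day blood, minimum = 14 + 6 = 20 days.
3. Baseline to surgery-day blood: shortest 6 - 0 = 6 days, longest 14 - (-14) = 28 days.
4. Surgery to post-op blood: shortest 23 - 14 = 9 days, longest 37 - 6 = 31 days. The lower limit is above zero, so this sample follows surgery in every patient.

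If day -14 itself counts as inside the two-week exclusion, the minima in steps 1 and 2 become 1 and 21 days. The conclusion is the same.

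**Intervals with fixed draws (day 0 before infusion; surgery day before induction)**

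- Last chemotherapy to baseline: at least 14 days.
- Baseline to surgery-day sample: 6 to 14 days, with no operation in between.
- Surgery to post-op sample: still 9 to 31 days.

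**Illustration of what an uncontrolled drift does to the test.** The documents give neither the size nor the direction of any drift, so these inputs are assumptions: pembrolizumab has no effect, the mean background change is *d* standard deviations of the within-patient change, and the test is a two-sided 5% paired t-test. With noncentrality *d*·√n, the chance of declaring a shift is:

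| n | d = 0.25 | d = 0.5 | d = 0.75 |
|---|---|---|---|
| 19 | 18% | 54% | 87% |
| 39 | 33% | 86% | 99.5% |

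The nominal rate is 5%. The two values of n are an assumed range for cohort B, whose size 8.1 does not fix: 40/70 of the 34 ER/PR-negative patients is about 19, and adding between none and all of the 20 ER-positive patients gives 19 to 39. The table shows how the test responds to a drift; it does not estimate the bias in this trial.

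**The case against.** Four points on the other side deserve weight.

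- **Zero days is a corner case.** Cohort B patients need imaging after chemotherapy, a new tumour biopsy, recovery of toxicity to Grade 1 or baseline, and a neutrophil count of at least 1,500/mcL. Consent must also precede any study blood draw or fresh biopsy. Together these make a draw within a day of chemotherapy less likely. This stands, and the typical gap is unknown. But none of these rules sets a minimum interval to the draw, and Table 1 has no lymphocyte criterion.
- **The surgery-day blood may well be pre-operative.** That visit also carries vital signs, physical examination and safety laboratory tests. This stands too: a reader might infer that surgical stress is present in this sample, and the documents do not support that. They leave the order open. Only the post-op sample is certainly after surgery.
- **A before/after comparison is specified.** Section 8.2 names paired tests, and 4.2.3.1 places T-cell subpopulations with the biomarker work. The gap is therefore narrower than a missing analysis: what is missing is which post-dose sample is used.
- **The root cause is the single-arm design, and fixed draw times do not cure it.** Correct. A day 0 baseline guarantees 14 days since chemotherapy, which reduces the influence of recovery without removing it.

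**Conclusion.** The point holds as one of timing and attribution. The stated windows allow a cohort B baseline with almost no interval after chemotherapy, against at least 20 days for the surgery-day sample, so lymphocyte recovery cannot be excluded as a cause of a shift in that cohort. The post-op sample follows surgery by 9 to 31 days in both cohorts and cannot isolate the drug. The day counts rest only on the plan's windows, with post-op days counted from the dose.

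A reader might go further and infer that any observed shift must reflect chemotherapy or surgery, or that the same shift would appear without pembrolizumab. The documents do not support this, because they give no size, direction or duration for such changes. In a cohort A patient whose surgery-day blood is drawn before the operation, neither mechanism applies to the baseline-to-surgery contrast. Nor can the share of the trial exposed to the chemotherapy problem be stated: 8.1 leaves cohort sizes open and gives no upfront-surgery versus neo-adjuvant split for ER-positive patients.

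The change is still worth making before further patients are enrolled, because analysis cannot recover a baseline drawn at the wrong time.

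**What to change.** 1. Amend the flow chart (2.2 and 6.0) and 5.2.2 so that the baseline central research sample is drawn on day 0 before the infusion. Day 0 lies inside the current screening window, and 5.2.4 already places dosing after the scheduled procedures.
2. State that the surgery-day research sample is drawn before induction of anaesthesia.
3. In 8.2, name the change between these two samples as the main test of the T-cell objective, reported separately for cohorts A and B. Record the date of last chemotherapy, so that days since chemotherapy can be shown or adjusted for in cohort B.
4. Present the post-op sample descriptively.
5. State as a limitation that residual chemotherapy recovery in cohort B cannot be separated from a drug effect without a control.

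The cost is a small schedule edit and the discipline of fixed draw times. No visit is added: the day 0 draw replaces the screening draw for this objective. Dose, eligibility and the washout rule are unchanged.
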